### **5.3 Secondary Efficacy Analyses**

The secondary efficacy variable is the investigator’s assessment of MMH using the MMPS (1 = minimal, 2 = mild, 3 = moderate, 4 = marked, 5 = very marked).

The proportion of responders will be analyzed with a responder defined as subjects who achieve an MMPS grade of  $\leq 3$ . The proportion of responders will be analyzed using Cochran-Mantel-Haenszel (CMH) tests stratified by baseline MMPS grade. In addition, 2-sided 95% confidence intervals for the treatment differences in response rates will be provided. Between group comparisons will only be performed for each BOTOX group against the placebo group, and for each BOTOX group against the next higher dose BOTOX group.

[REDACTED]

[REDACTED]

[REDACTED]

[REDACTED]

[Redacted text block]

[Redacted text block]

[Redacted text block]

[Redacted text block]

[Redacted text block]

[Redacted text block]

[Redacted text block]

[Redacted text block]

[Redacted text block]

[Redacted text block]

[Redacted text block]

[Redacted text block]

[Redacted text block]

[Redacted text block]

[Redacted text block]

[Redacted text block]

[Redacted text block]

[Redacted text block]

[Redacted text block]

[Redacted text block]

[REDACTED]

[REDACTED]

[REDACTED]

[REDACTED]

[REDACTED]

[REDACTED]

[REDACTED]

## **6.1 Exposure to Study Treatment**

Subjects' exposure to BOTOX will be summarized by number of treatments received.

## **6.2 Adverse Events**

Adverse events will be coded from the verbatim text into preferred term (PT) and the primary system organ class (SOC) by using the MedDRA dictionary.

Adverse events are collected both for the screening/baseline period pretreatment (which are referred to as pretreatment AE) and for the followup period after treatment is initiated (which are referred to as postbaseline AE).

A treatment emergent adverse event (TEAE) is an adverse event with onset after the initiation of study treatment, or an adverse event with onset prior to study treatment that worsened in severity, or became serious after the initiation of study treatment.

A TEAE for a specific treatment cycle is an adverse event with onset after the initiation of study treatment for the specific cycle, or an adverse event with onset prior to the cycle that worsened in severity during the cycle, or became serious after the initiation of study treatment for the specific cycle.

In each of the analysis periods (entire study or by treatment cycle), a specific TEAE will only count once per subject, associated with its worst severity during the time period of interest. Unless stated otherwise, the methods of analyses described in this section will be applied to each of the screening/baseline and study period.

The MedDRA nomenclature will be used to code all adverse events. Three summary tables as shown below will be presented for TEAEs, and for a subset of TEAEs that were considered by investigator to be treatment related (ie, treatment related TEAEs).

The 3 summary tables to be generated are:

1. by preferred term in descending order of incidence rate (summarized by treatment group)
2. by preferred term within primary SOC in alphabetical order (the incidence rates of each preferred term within a primary SOC as well as overall primary SOC incidence rates will be summarized by treatment group. Primary SOC's will appear alphabetically and preferred terms within each primary SOC will be sorted by descending incidence of adverse events. If a subject has multiple reports coded to the same preferred term within a primary SOC, that subject will be counted only once for that preferred term within that primary SOC).
3. by maximum severity of preferred term within primary SOC in alphabetical order (the incidence rates of the maximum severity of each preferred term within a primary SOC will be summarized by treatment group. Primary SOC's will appear alphabetically and preferred terms within a primary SOC will be sorted in descending incidence of adverse events. If a subject has multiple reports coding to the same preferred term within a primary SOC, the maximum severity for that subject will be used and that subject will be counted only once for that preferred term within that primary SOC.)

TEAEs and treatment-related TEAEs will be summarized for each treatment regimen by treatment cycle and over the entire study.

All adverse events leading to study discontinuation, treatment-related adverse events leading to study discontinuation, and serious adverse events leading to study discontinuation will be summarized by preferred term within primary SOC. A listing of all adverse events leading to study discontinuation will be provided.

A subject listing will be generated for all adverse events, including subject age, sex, and race, primary SOC, preferred term, onset and stop date, onset day relative to the most recent dose, relationship, and severity.

A listing of all pretreatment AEs (PTAEs) will be provided.

### **6.3 Serious Adverse Events**

A serious adverse event is defined as any adverse event occurring at any dose that results in any of the following outcomes: death, a life-threatening adverse event, inpatient hospitalization or prolongation of existing hospitalization, a persistent or significant disability/incapacity, or a congenital anomaly/birth defect. Important medical events that may not result in death, be life-threatening, or require hospitalization may be considered a serious adverse event when, based upon appropriate medical judgment, they may jeopardize the patient or subject and may require medical or surgical intervention to prevent 1 of the outcomes listed in this definition. All cancer adverse events are considered serious adverse events by Allergan. Allergan also considers all abortions, spontaneous, or elective as serious adverse events.

Serious TEAEs will be summarized similar to TEAEs for entire study, and by treatment cycle. A subject listing will be generated with serious adverse events including subjects' age, gender, race, onset day, duration (number of days the adverse event lasted), relationship to study treatment, and serious criteria (congenital anomaly, death, hospitalization, life-threatening, significant disability, and other).

### **6.4 Adverse Events Possibly Associated with Effects Remote to Site of Injection (Possible Spread of Toxin, PSOTs) and Local Effects**

Possible distant spread of toxin is defined as a possible pharmacologic effect of botulinum toxin at sites noncontiguous and distant from the site of injection. Possible spread of toxin (PSOT) is defined as those events classified as possible distant spread of toxin and locally-occurring adverse events that could be due to a possible pharmacologic effect of botulinum toxin. In order to retrieve cases potentially meeting this definition, the steps outlined below are employed. This analytic methodology is approved by the Allergan Reference Member State that reviews the PSURs, is the current standard utilized in PSURs, and was agreed with the US FDA.

The index search MedDRA preferred terms identified for the possible distant spread of toxin analysis were originally based upon individual reported symptoms of the naturally occurring condition of clinical botulism ([Merck Manual](#), [Beers, 2006](#)). It was acknowledged that possible local effects may also occur anatomically proximal to the injections site, such as ipsilateral ptosis

following injection for strabismus, or dysphagia following injection for cervical dystonia. The preferred terms used in this analysis were purposely chosen to be broad, knowing that cases would subsequently be further characterized. These 39 preferred terms are listed in [Table 2](#) below.

**Table 2 MedDRA Version 20.1 Preferred Terms Evaluated for Possible Spread of Toxin**

Cardiac Disorders Bradycardia
 
Eye Disorders Accommodation disorder Diplopia Extraocular muscle paresis Eyelid function disorder Eyelid ptosis Pupillary reflex impaired Vision blurred
 
Gastrointestinal Disorders Constipation Dry mouth Dysphagia Ileus paralytic
 
Infections and Infestations Botulism
	
Musculoskeletal and Connective Tissue Disorders Muscular weakness
 
Nervous System Disorders Bulbar palsy Cranial nerve palsies multiple Cranial nerve paralysis Dysarthria Facial paralysis Facial paresis Hyporeflexia Hypotonia Paralysis Paresis cranial nerve Peripheral nerve palsy Peripheral paralysis Speech disorder Vocal cord paralysis Vocal cord paresis
	
Renal and Urinary Disorders Urinary retention
 
Reproductive System and Breast Disorders Pelvic floor muscle weakness
 
Respiratory, Thoracic and Mediastinal Disorders Aspiration Diaphragmatic paralysis Dysphonia Dyspnoea Pneumonia aspiration Respiratory arrest Respiratory depression Respiratory failure

---	--	--

*Step 1.* Adverse event listings will be searched for cases (regardless of seriousness, listedness, or medical confirmation) mapping to the 39 MedDRA preferred terms from [Table 2](#).

*Step 2.* In order to focus on the most informative cases, reports meeting the criteria in Step 1 together with abnormal neurologic findings recorded on a NEF will then be medically reviewed and placed into 1 of the following categories. Where cases containing elements of more than 1 category, medical judgment will be applied to determine the most significant factor in the case, and placed into 1 category accordingly. These categories are:

- a. *Insufficient Information:* Cases considered insufficiently documented for medical assessment or discussion of possible spread of toxin will not be further reviewed in this analysis, but additional information will be requested in follow-up as appropriate.
- b. *Inconsistent with Pharmacology of Botulinum Toxin Effects:* Cases that reported a clinical course of events inconsistent with the pharmacology of botulinum toxin (eg, rapidly fluctuating signs and symptoms, increasing spasticity) will not be reviewed further in this

analysis. Specific note is made of the constitutional symptoms (Peters 2005) that have been reported as soon as within hours of treatment. These include complaints of generalized fatigue, flu-like symptoms, dizziness, asthenia, nausea, etc. These constitutional symptoms are not accepted as due to possible spread of toxin in this analysis of neurologic symptoms. Hypersensitivity events, are immunologic rather than pharmacologic and are not consistent with the definition of PSOT.

- c. *Localized Neuromuscular Weakness:* Cases reporting only locally occurring events relative to the site of injection will be captured separately for this analysis.
- d. *Confounded Cases:* Cases reporting events that are more likely attributed to other medications and/or underlying medical conditions will not be reviewed further in this analysis.
- e. *Remaining Cases:* Cases not meeting the criteria above will be analyzed further. These remaining cases will then be subjected to an aggregate reassessment according to Step 3.

*Step 3.* Allergan will apply additional medical context to the evaluation of the remaining cases to increase precision of the analysis. This will be done by taking into consideration the clinical presentation of neurological signs and symptoms in individual case reports, with forethought to the known clinical presentation of foodborne and wound botulism. Cases not considered to be clinically related to PSOT include presentations with no neurologic signs or symptoms distant from the site of injection and, therefore, will be candidates for exclusion.

Any remaining cases subsequent to the Step 3 analysis will be further described, including case narratives and concluding observations. In addition, cases with localized neuromuscular weakness (local spread of toxin) will have been identified in Step 2c. The incidence of PSOT TEAE identified in Step 1 will be summarized by preferred term in descending order of incidence rate for the entire study, and for each treatment cycle.

## **6.5 CT Scan Safety Measures**

Using a standardized protocol, CT scans for each subject will be captured by a CT technologist at screening (baseline), treatment cycle 1 day 90, and the exit visit, and the 9 measures listed below will be assessed by a central reader.

For each of the quantitative measures, summary statistics will be presented for baseline, mean change from baseline, and percent change from baseline (sample size, mean, standard deviation, median, minimum, and maximum) by treatment regimen for all scheduled visits.

For each of the qualitative measures, the incidence of change from baseline will be summarized on a per-subject basis. Interpretation of change from baseline will be provided by the central reader in comments.

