#### **General Statistical Methods and Types of Analyses:**

Three analysis populations will be used:

- The modified intent-to-treat (mITT) population will consist of all randomized subjects who received study treatment and had at least 1 follow-up visit. The analysis will be based on the actual treatment subjects received.
- The per-protocol (PP) population will consist of randomized subjects who have no significant deviations from the protocol. Key criteria will be determined prior to database lock.
- The safety population will consist of all subjects who are treated with at least 1 injection of study treatment.

Day 1 will be considered as baseline for all measures except for the dental examination and CT imaging, for which the screening visit will be considered baseline. The primary efficacy variable will be lower facial volume at day 90. The change from baseline in lower facial volume will be analyzed by analysis of variance (ANOVA) with treatment and baseline MMPS grade as factors to assess the response between each BOTOX dose compared with placebo.

For analysis of the mITT population, the last observation carried forward (LOCF) method will be used to impute missing values. For analysis of the PP population, observed data without imputation will be used.

For each cohort, there will be a database snapshot with key data through the day 90 visit, for the purpose of the DRC assessment. There will be a final database lock with all study data after all subjects have completed the study (final cohort day 360). Subjects' treatment assignment will remain blinded for all site personnel, study subjects, and Allergan personnel directly involved with ongoing operational activities of the clinical study, until completion of the final database lock.

Data will be summarized with descriptive statistics, frequency tables, and data listings. Categorical variables will be analyzed using Fisher's exact tests, Pearson's chi-square tests, or Cochran-Mantel-Haenszel (CMH) tests as appropriate. Continuous variables will be analyzed using t-test, analysis of covariance (ANCOVA), or corresponding nonparametric methods.

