In the medical literature, most side effects associated with BOTOX treatment of MMH have been local and expected, based on the well-established safety profile of BOTOX and the muscles injected. Adverse events reported in the medical literature include pain, discomfort, or muscle ache at the sites of injection; masticatory difficulties; speech disturbances; and cosmetic complaints related to the masseter and/or adjacent facial muscles. Typically, these events have been reported within 2 weeks posttreatment, were mild to moderate in severity, and resolved within 1 to 3 months. For further details regarding the safety of BOTOX treatment of MMH, including a comprehensive summary of the published literature reporting treatment in > 350 patients, please refer to the Investigator's Brochure.

This study is designed to evaluate the safety and efficacy of different doses of BOTOX for the treatment of MMH, to identify potential effects on associated structures (mandible and teeth), and to assist in the design of future clinical studies.

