### **2.3.1 Treatment Group and Treatment Cycles**

A treatment cycle is considered to start on the day of treatment with study medication and end on the day prior to the next study treatment or on the study exit day if there are no subsequent treatments.

Between group comparisons will only be performed for each BOTOX group against the placebo group, and for each BOTOX group against the next higher dose BOTOX group.

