### **2.3.2 Baseline, Changes from Baseline and Direction of Differences**

The latest measurement taken on or before day 1 prior to the first injection will be the baseline measurement. In addition, within each treatment cycle, “cycle baseline” is defined as the most recent evaluation prior to the current cycle’s treatment. Changes from baseline will be based on the day 1 baseline (rather than cycle baseline) unless otherwise stated.

Change from baseline will be calculated as followup minus baseline. The interpretation of a positive or negative change from baseline is specific to the outcome measure and will be discussed as needed. Treatment differences will be reported as BOTOX minus placebo and as BOTOX (higher total dose) minus BOTOX (lower total dose).

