### **2.3.8 Confidence Intervals**

For dichotomous variables, 2-sided 95% confidence intervals for proportions will be calculated based on the normal distribution approximation, unless otherwise stated.

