#### *Quantitative Safety Measures*

1. bigonial width (mm)
2. cortical thickness under the insertion point of the masseter muscle at the mandibular ramus (mm) (left and right)
3. mandibular flare angle (degrees; left and right)
4. gonial angle (degrees; left and right)

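### SAP 6.5 prespecifies no placebo-controlled estimate with an interval for the quantitative CT measures, and no randomised comparison at exit

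*SAP*

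**What the plan says.** SAP 6.5 lists four quantitative measures read centrally from CT: bigonial width, cortical thickness under the masseter insertion, mandibular flare angle and gonial angle. The last three are taken on left and right. The planned analysis is: "For each of the quantitative measures, summary statistics will be presented for baseline, mean change from baseline, and percent change from baseline". The statistics are N, mean, SD, median, minimum and maximum for each regimen. CT is done at screening, cycle 1 day 90 and exit. At the end of SAP 6.5 the exit scan is divided in two: once-treated subjects appear under a cycle 1 exit, twice-treated subjects under a cycle 2 exit.

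The general conventions do not add a contrast:

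- SAP 2.3.1 limits the pairs that may be compared: "Between group comparisons will only be performed for each BOTOX group against the placebo group", and each dose with the next higher one.
- SAP 2.3.2 fixes the direction of any difference, not which variables get one.
- SAP 2.3.8 covers proportions: "For dichotomous variables, 2-sided 95% confidence intervals for proportions will be calculated based on the normal distribution approximation".
- SAP Amendment 1 removed p-values from the safety section.

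By contrast, SAP 5.2 and 5.3 plan treatment differences with 95% intervals for facial volume and MMPS response.

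Protocol Section 1 gives as one purpose of the study "to identify potential effects on associated structures (mandible and teeth), and to assist in the design of future clinical studies". Section 1.3 says the CT and dental examinations were designed for that purpose, and also calls the CT measures exploratory. No margin is stated.

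**The concern.** An arm's mean change from baseline contains any treatment effect plus anything common to all arms, such as reader drift or remeasurement error. The documents give no reproducibility figure for the CT measures, so the size of that component is unknown. The placebo difference removes what is common, and its interval separates a small effect from an imprecise estimate. The plan collects the data for both but specifies neither.

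The exit display raises a second problem. Under Protocol 5.10, a second treatment requires, among other things, an MMPS grade of at least 4 at day 180. That grade is measured after randomisation and is expected to respond to treatment. Twice-treated BOTOX subjects are therefore partly selected for poor or short-lived response, while placebo subjects are selected differently. Comparing arms within either subset is not a comparison of randomised groups, yet these are the only exit summaries planned. Exit is also the longest follow-up for bone.

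**Working it through.** **Inputs.** Protocol 7.5: 40 BOTOX and 10 placebo per cohort. Protocol Table 2: four cohorts with one dose each, so 40 placebo subjects if pooled. SAP Section 5 states pooling for efficacy; using it for CT is an assumption. No CT SD is given, so results are in SDs of the change score.

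**The plan's own figure.** Protocol 7.5 gives 93% power for facial volume (effect size 1, 1-sided 0.10, 40 v 10). The standard error is sqrt(1/40 + 1/10) = 0.354 and 1/0.354 = 2.83. The normal approximation gives Φ(2.83 − 1.28) = 93.9%, and the noncentral t with 48 df gives 93.6%. The figure reproduces. It does not concern CT, for which no precision is stated.

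**Unadjusted 95% half-width:** t(0.975, df) × sqrt(1/n1 + 1/n2).

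| Comparison | Half-width (SD of change) |
|---|---|
| 40 v 40, two arms only (78 df) | 1.991 × 0.2236 = 0.445 |
| 40 v 40, error df from all arms (194) | 1.972 × 0.2236 = 0.441 |
| 40 v 10, one cohort only (48 df) | 2.011 × 0.3536 = 0.711 |
| 36 v 36 (10% of scans lost, assumed) | 0.470 |
| 32 v 32 (20% of scans lost, assumed) | 0.500 |

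**Effect of a cohort term**, for the planned 200 subjects with MMPS grade balanced across arms. Each dose occurs in one cohort only.

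- Categorical cohort: each dose is compared only with its own 10 placebo subjects. Half-width 1.972 × 0.3536 = 0.697.
- Numeric cohort (the form in the SAP 5.2 sensitivity model): the slope comes from placebo alone. The variance is 1/40 + 1/40 + (c − 2.5)²/50, where 50 = 10 × (2.25 + 0.25 + 0.25 + 2.25). For 24 U and 96 U: 1.972 × sqrt(0.095) = 0.608. For 48 U and 72 U: 1.972 × sqrt(0.055) = 0.463.

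**Baseline adjustment** multiplies the half-width by sqrt(1 − ρ²), where ρ is the correlation of change with baseline (assumed). At ρ = 0.3 the factor is 0.954, about 5% narrower. At ρ = 0.5 it is 0.866, about 13% narrower. With equal variances at both visits, 1 − ρ² = (1 + r)/2, where r is the baseline-to-follow-up correlation. If r were 0.95, the factor would be 0.987, a gain of about 1%.

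**Exit subsets.** Suppose 10 to 20 of 40 BOTOX and 30 to 36 of 40 placebo subjects were retreated (assumed). The half-width would be 0.56 to 0.74 SD in the cycle 2 exit group and 0.74 to 1.14 SD in the cycle 1 exit group, before considering selection. Combined by day 1 treatment, it returns to about 0.44 SD with complete scans.

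**Number of intervals.** With sides separate there are 1 + 3 × 2 = 7 variables, so 7 × 4 doses × 2 visits = 56 intervals, of which 56 × 0.05 = 2.8 would be expected to exclude zero by chance if no effect existed. With sides averaged, 4 × 4 × 2 = 32 intervals and 1.6 expected.

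**The case against.** A reader might infer that the trial will be unable to say what change in bone it excludes. The documents do not support that. N, mean and SD of change per regimen suffice for an unadjusted day 90 difference and interval. The same summaries for the two exit subsets could be recombined by arithmetic into an unadjusted exit contrast. What cannot be recovered is baseline adjustment. If left and right are tabulated separately, the SD of a per-subject average is also lost: SAP 2.3.5 averages sides for angles and MMPS but gives no rule for cortical thickness.

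A reader might also infer that the SAP departs from the protocol, whose summary says "Continuous variables will be analyzed using t-test, analysis of covariance (ANCOVA), or corresponding nonparametric methods". That sentence is a generic menu, not tied to CT, in a paragraph that begins with descriptive summaries. It does not establish a departure.

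Other objections stand in part:

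- The measures are labelled exploratory, no margin is set and safety p-values were deliberately removed. Descriptive reporting is consistent with this, so the point concerns informativeness. Estimates with intervals fit the same label.
- Drift common to all arms would show in the placebo row. A reader would still have to subtract and judge uncertainty unaided.
- Protocol 1.3 lists bigonial width, flare angle and gonial angle under facial shape. Only cortical thickness, of these four, is listed as an indicator of bone structure.
- Part of the SAP between 5.3 and 6.1 is redacted and may hold CT efficacy comparisons. The safety plan in 6.5 is visible and has none.

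**Conclusion.** The point holds as a gap in prespecification. For the quantitative CT measures, the visible plan contains no placebo-controlled estimate with an interval and no randomised comparison at exit; both would otherwise be left to post hoc calculation without baseline adjustment. The attainable 95% half-width before adjustment is about 0.44 SD of the change per dose with pooled placebo, and about 0.70 SD against a dose's own cohort placebo. A dose with an observed difference of zero would thus still be compatible with a mean shift of that size in either direction. These figures assume full enrolment and complete scans; the pooled figure also assumes that placebo cohorts can be combined for CT. Without an SD they cannot be converted to millimetres or degrees. Baseline adjustment would bring a modest gain, and almost none if the measures are very stable within subjects. This is an inexpensive improvement on a stated study purpose, not a contradiction within the documents.

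**What to change.** In SAP 6.5, keep the descriptive tables and add, for each quantitative measure at day 90 and at exit, the BOTOX-minus-placebo difference in change for each dose with a 2-sided 95% CI and no p-value.

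- **Model:** ANCOVA with treatment, baseline MMPS grade and the baseline value of the same measure; placebo pooled; subjects grouped by day 1 treatment.
- **Exit:** combine once-treated and twice-treated subjects for this comparison, and keep the present split as a descriptive display.
- **Sides:** average left and right within subject, and state this for cortical thickness, which has no rule now.
- **Lead measure:** cortical thickness.
- **Cohort:** leave it out of the main model and report a cohort-adjusted model as a sensitivity analysis, noting the wider intervals.

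The cost is a few sentences in the SAP and one table from data already collected. The downside is that the intervals will be wide and about 32 will be reported without multiplicity control, so the table must be labelled exploratory estimation only.

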The present study includes CT and dental examinations developed by Allergan with input from consultants and specifically designed to identify potential effects of BOTOX treatment of MMH on the mandible and teeth. The CT scan captured by a CT technologist will be transferred to a central reader, who will review it to assess for changes in lower facial shape (masseter muscle volume, bigonial width, mandibular flare angle, and gonial angle) as well as relevant indicators of change in bone structure (mandibular condylar head shape, mandibular condylar cortical surface, mandibular condylar head, mandibular condylar position, glenoid fossa/eminence, and cortical thickness under the insertion point of the masseter muscle at the mandibular ramus). The dental examination will be conducted by a dentist to assess for any potential changes in dentition, occlusion, and overall oral health (Attachment 12.1.7). Both CT and dental measures will be taken at screening (considered as baseline), day 90, and at study exit (day 360 or study discontinuation).

In summary, the data obtained from this study will be used to develop a better understanding of the safety and efficacy of different dose regimens of BOTOX for the treatment of MMH.

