#### *Qualitative Safety Measures*

1. mandibular condylar head shape (A-L)
2. mandibular condylar cortical surface (Yes or No)
3. mandibular condylar head (Regular, Thin, Thick)
4. mandibular condylar position (A-J)
5. glenoid fossa and articular eminence (Yes or No)

CT scan is only done at screening (baseline), treatment cycle 1 day 90 and the exit visit. For the CT safety measurements, the exit visit will be displayed as treatment cycle 1 exit visit and treatment cycle 2 exit visit. Only subjects who received the second injection will be included in the treatment cycle 2 exit visit. Subjects who received only 1 treatment will be included in the treatment cycle 1 exit visit.

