## **6.6 Dental Examination**

Dental history will be coded using the Medical Dictionary for Regulatory Activities (MedDRA) dictionary. A subject listing will be generated for the dental history.

For each dental measurement, the incidence of normal, abnormal not clinically relevant, and abnormal clinically relevant will be summarized by visit. Interpretation of any measurement noted as abnormal not clinically relevant will be provided by the dentist in comments.

Shift table will also be provided for post baseline dental examination vs baseline examination.

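### The planned table for the five qualitative CT bone measures cannot separate new abnormalities from reversals by arm, so a bone-safety signal may be obscured

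*SAP*

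**What the plan says.** SAP 6.5 splits the CT safety measures into four quantitative and five qualitative ones. For the quantitative measures, "summary statistics will be presented for baseline, mean change from baseline, and percent change from baseline", by treatment regimen and visit, so the sign of the change is kept. For the qualitative measures the whole plan is two sentences: "For each of the qualitative measures, the incidence of change from baseline will be summarized on a per-subject basis", and "Interpretation of change from baseline will be provided by the central reader in comments".

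The five qualitative measures are condylar head shape (categories A to L), condylar cortical surface (Yes/No), condylar head (Regular, Thin or Thick), condylar position (A to J), and glenoid fossa with articular eminence (Yes/No). Scans are taken at screening, at day 90 of cycle 1 and at exit. The exit scan is displayed under cycle 1 or cycle 2 according to whether the subject was retreated.

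The companion safety examination is treated differently. For dental findings, SAP 6.6 adds: "Shift table will also be provided for post baseline dental examination vs baseline examination". The visible text has no such table for CT.

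**The concern.** Protocol 1.3 says the CT and dental examinations were "specifically designed to identify potential effects of BOTOX treatment of MMH on the mandible and teeth", and that it is not known whether such effects occur. It names six CT indicators of bone structure. Five of them are the qualitative measures above; only cortical thickness is quantitative. The undirected count therefore governs most of the bone-structure results.

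For categorical findings, an incidence of change does not say what changed into what. A condylar head going from Regular to Thin and one going from Thin to Regular each add one subject to the numerator. So does a repeat read that lands in a different category. SAP Amendment 1 removed p-values from the safety analysis, so the descriptive tables are the by-arm evidence. If they do not show direction, a sponsor or regulator comparing doses with placebo cannot tell whether a given percentage reflects new abnormality.

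**Working it through.** **1. Is there a figure in the plan to reproduce?** Not for this point. The only power statement (Protocol 7.5: 40 vs 10, effect size 1, 1-sided 0.10, 93%) concerns lower facial volume. It reproduces (93.6% by noncentral t with 48 degrees of freedom) but has no bearing on CT. The documents give no rate of qualitative CT change and no repeatability figure for the central reader. Every rate below is an assumption.

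**2. What the statistic can and cannot show.** Write w for the proportion of subjects moving away from normal and b for the proportion moving back. The table reports w + b. Different pairs (w, b) give the same sum:

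- dose: w = 15%, b = 5%, total 20%. With 40 subjects this is 6 + 2 = 8.
- placebo: w = 10%, b = 10%, total 20%. With 40 pooled placebo subjects (4 × 10; pooling is stated for efficacy and assumed here) this is 4 + 4 = 8.

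Both arms show 8 of 40 changed, although worsening differs by 5 points.

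**3. Background flips that simply add.** Let f be the flip rate in each direction, the same in both arms, and a the extra new abnormality on a dose. Any-change is 2f + a on the dose and 2f on placebo; worsening is f + a and f.

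| f | a | Any-change, dose vs placebo | Ratio | Worsening, dose vs placebo | Ratio |
|---|---|---|---|---|---|
| 5% | 10% | 20% vs 10% | 2.0 | 15% vs 5% | 3.0 |
| 10% | 10% | 30% vs 20% | 1.5 | 20% vs 10% | 2.0 |

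The absolute difference is a = 10 points in every comparison. Only the ratio moves. The worsening count still contains f, the flips toward abnormal.

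**4. Background change that overlaps with true change.** Let p be the rate of new abnormality and q the rate of other change, independent of p and equal across arms. Any-change is p + (1 − p)q, so the difference between arms is (p₁ − p₀)(1 − q). With p₀ = 5% and p₁ = 20%:

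| q | Placebo | Dose | Difference (points) | Ratio |
|---|---|---|---|---|
| 0% | 5.0% | 20.0% | 15.0 | 4.00 |
| 5% | 9.75% | 24.0% | 14.25 | 2.46 |
| 10% | 14.5% | 28.0% | 13.5 | 1.93 |
| 20% | 24.0% | 36.0% | 12.0 | 1.50 |
| 30% | 33.5% | 44.0% | 10.5 | 1.31 |

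At q = 0 nothing is lost. Whether the absolute difference shrinks at all depends on which model holds, and the documents do not allow a choice between them.

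**5. Would full shift grids work for all five?** No. A to L gives 12 × 12 = 144 cells and A to J gives 10 × 10 = 100 cells, for about 40 subjects per dose. The Yes/No measures need 2 × 2 = 4 cells and condylar head needs 3 × 3 = 9.

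**The case against.** The strongest reply is that an undirected screen is reasonable here. The CT measures are described as exploratory, no harmful direction was specified in advance, and the letter categories have no visible order. The central reader interprets each change. The quantitative measures keep their sign, and the Data Review Committee, whose outside clinicians come from dentistry, radiology or oral surgery, sees cumulative safety data through day 90. This stands as a reason to keep the incidence of change. It does not supply what is missing. The comments have no stated coding or tabulation by arm, the signed measures are different measures, and the committee's day 90 review does not cover the exit scans.

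A second reply is that SAP 6.5 is silent on direction and does not rule it out; SAP 2.3.6 provides counts and percentages for categorical variables, which could include category frequencies. That is fair. A reader might infer that the SAP expressly ignores direction, but it does not say so. The undirected count is the natural reading of the one statistic named. Category frequencies by visit would show net movement but not within-subject transitions.

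A third reply is that few subjects may have room to improve: entry is limited to ages 18 to 50, and a history of temporomandibular joint disorder is excluded. This stands. If reversals are rare and reads repeatable, any-change and worsening nearly coincide. The masking example in the working also needs less improvement on the dose than on placebo, for which the documents offer no mechanism.

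Finally, what Yes/No, A to L and A to J mean cannot be read from the visible text, so worsening cannot yet be coded for those items.

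**Conclusion.** The point holds as a gap in reporting. The planned by-arm statistic for five of the six bone-structure indicators cannot separate new abnormalities from reversals, and the interpretation that could do so is not tabulated. A bone-safety signal may therefore be obscured.

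Two stronger readings are tempting and unsupported. The first is that a signal is in fact diluted. That needs non-zero reversal or reclassification, for which the documents give no rate; under the additive model the absolute difference does not change. In the assumed cases the ratio falls from 3.0 to 2.0 or from 2.0 to 1.5 (additive), or from 4.0 to between 2.46 and 1.31 (overlapping, q from 5% to 30%). These illustrate the mechanism and do not estimate its size, which cannot be determined from the documents. The second is that directional counts would remove central-reader error. They would not, because flips toward abnormal remain in them.

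The signed analyses, including cortical thickness, are unaffected. The change is worth making because it is cheap and the SAP already uses the same tool for dental findings.

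**What to change.** In SAP 6.5, keep the per-subject incidence of change and state that it is given by treatment regimen and visit, as for the quantitative measures. Add, by treatment regimen, at day 90 and at the cycle 1 and cycle 2 exit displays:

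- shift tables of baseline by post-baseline category for cortical surface, condylar head, and glenoid fossa/eminence;
- a compact tabulation of the transitions actually observed for condylar head shape (A to L) and condylar position (A to J), in place of full grids;
- where a normal reference category is defined before unblinding, the incidence of change away from it and of change toward it, shown separately.

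The cost is SAP wording, agreement on reference categories where they can be defined, and a few more descriptive tables, some of them sparse. All of it uses data already collected, with no new scans or reads.
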